This will be a 4 arm randomized controlled trial among 206 smokers who are patients at Massachusetts General Hospital and who receive primary care from a Partners primary care provider. Patients will be proactively recruited from MGH primary care practices. Patients will also be recruited from online advertisements on the Partners Clinical Trials website, from among MGH primary care patients who consent to participate in Research Offers Direct to You, and by referral from the MGH inpatient Tobacco Treatment Service counselors. We will recruit both smokers who are ready to quit smoking in the next 30 days and those who are not planning to quit in the next 30 days. The text message program is tailored to readiness to quit. For those ready to quit in the next 30 days, they will be sent messages based on the SmokeFreeTXT content. For those not ready to quit, we have developed content including motivational advice and tips to try a practice quit attempt for a few hours or days.⁵³ The text message program will also include medication adherence support text messages based on the Information-Motivation-Behavioral Skills model of adherence.⁵⁴ Combination NRT is first-line therapy which is more effective than nicotine patch alone and will be offered to daily smokers, dosed per package instructions.²¹ Smokers who are not ready to quit and who are randomized to one of the two nicotine medication arms will be offered one box of lozenges to try in a practice quit attempt.⁵³

The RC will not be blinded to treatment assignment because he/she will register subjects randomized to the text messaging arms in the text messaging program during the enrollment telephone call to verify receipt of an enrollment confirmation text message ("Hi [First name] Welcome to getReady2Quit (R2Q). Your messages and ratings will start soon. Reply STOP to quit, HELP for info. Msg&DataRatesMayApply"). Randomization will be done by a computer generated random sequence.

b. Procedures for obtaining informed consent (including timing of consent process)

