- Any prior use of behavioral treatment for smoking cessation (clinic or class, in-person counseling, telephone counseling, text messaging, alternative therapy, self help materials, or online communities and applications)
- Past month use of other tobacco products-cigars, cigarillos, smokeless tobacco, hookah, or e-cigarette

Motivation to quit, confidence to quit, and perceived 2-week distress measured using single-item instruments with 11-item likert scale

- Readiness to quit⁶⁶
- Measures of psychosocial mechanisms targeted by the text messaging
- PHQ-2 and GAD-2 screening for depression and anxiety
- Single item alcohol⁶⁷ and substance use disorder⁶⁸ screening questions and past month illegal use of drugs⁶⁹
- On an average day, about how many text messages do you send and receive on your cell phone?
- Cell phone carrier, type (smartphone) and plan details (pay per text or unlimited text messaging).
- Email for subjects that want the follow up surveys emailed
- Social security number for payment purposes

Outcome assessments:

Medication use outcomes will be assessed by telephone interview at week 1 and 2 by a second research coordinator blinded to treatment assignment: number of days patch was used in the last week and number of lozenges used each of the last two days. These will be used to calculate total duration of medication.⁷⁰.

1 & 2 week telephone outcome assessments

- Have you used nicotine patch in the past 7 days?
 - How many days in the past week did you use a nicotine patch?
- Have you used nicotine lozenges in the past 7 days?
 - How many days in the past 7 days did you use a nicotine lozenge?
 - On days when you use lozenge, how many do you use on average?
- Since starting the study, have you stopped smoking cigarettes for 1 day or longer because you were trying to quit smoking?
 - If yes→On how many of the past 7 days did you have at least one cigarette?
If 0→Have you smoked cigarettes, even a puff in the past 7 days?
- Have you experienced any side effects in the last 7 days from quit smoking medications?
- Receipt of text messages since last assessment.
- *Only Week 2*→ Would you like more nicotine medication? A refill request would be sent to your PCP and it will be billed through your regular insurance.

6 week telephone outcome assessments

- Have you used nicotine patch in the past 7 days?
 - How many days in the past week did you use a nicotine patch?
- Have you used nicotine lozenges in the past 7 days?

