 - How many days in the past 7 days did you use nicotine lozenges?
 - On days when you use lozenge, how many do you use on average?
- Since starting the study, have you stopped smoking cigarettes for 1 day or longer because you were trying to quit smoking?
 - If yes→In the past 30 days, how many days did you not smoke cigarettes?
 - If yes→On how many of the past 7 days did you have at least one cigarette?
If 0→Have you smoked cigarettes, even a puff in the past 7 days?
- Have you experienced any side effects in the past 30 days from quit smoking medications?
- Receipt of text messages since last assessment

12 week end-of-treatment telephone outcome assessment

Quit attempt and smoking cessation outcomes will be assessed by telephone at 12 weeks (end of treatment)

PRIMARY OUTCOME: Self-reported quit attempt in the last 12 weeks defined as intentional not smoking for 24 hours or more ("Since the start of the study, have you quit smoking intentionally for 1 day or longer" in addition to past follow up reports of quit attempts). We recognize that tobacco abstinence for more than one day is the desired outcome but feel this intermediate outcome is appropriate in the context of a pilot study with limited resources.

SECONDARY OUTCOMES:

How many times did you try to quit during the study?

Have you smoked, even a puff, in the past 7 days? (7 day PPA)

In the past 30 days, how many days did you not have a cigarette?

How many cigarettes do you now smoke per day?

Motivation to quit, confidence to quit, and perceived 2-week distress measured using single-item instruments with 11-item likert scale

Use of evidence based treatment and behavioral treatment in the past 12 weeks (NRT, varenicline, bupropion, clinic or class, in-person counseling, telephone counseling, text messaging, alternative therapy, self help materials, or online communities and applications)

Past month use of other tobacco products including electronic cigarettes

Side effects of quit smoking medications in the past 12 weeks

Satisfaction with treatment

Exhaled CO in ppm among subjects reporting 7 day PPA

Up to 10 attempts will be made to reach study subjects for each outcome assessment (weeks 1, 2, 6 and 12).

Measures of intervention utilization:

Intervention utilization will be obtained from MobileCommons software.

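### Assessor blinding is stated only for medication use at weeks 1 and 2, those calls include an item that can reveal text-messaging allocation, and no blinding is stated for the week-6 and week-12 calls that feed the primary outcome

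*Combined protocol and SAP*

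**What the plan says.** The protocol mentions assessor or staff blinding in two places.

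- Section IV.a (enrolment): "The RC will not be blinded to treatment assignment because he/she will register subjects randomized to the text messaging arms" in the messaging platform during the enrolment call.
- Section V.d (Outcome assessments): "Medication use outcomes will be assessed by telephone interview at week 1 and 2 by a second research coordinator blinded to treatment assignment".

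The item list for weeks 1 and 2 follows the second statement directly. In order, it covers patch and lozenge use, then the quit-attempt question ("Since starting the study, have you stopped smoking cigarettes for 1 day or longer because you were trying to quit smoking"), then side effects, then "Receipt of text messages since last assessment". The week-6 list also ends with the text-message item.

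For the end of treatment, Section V.d says "Quit attempt and smoking cessation outcomes will be assessed by telephone at 12 weeks (end of treatment"), without saying who calls or whether that person knows the allocation. The endpoint is given as "PRIMARY OUTCOME: Self-reported quit attempt in the last 12 weeks defined as intentional not smoking for 24 hours or more", and the week-12 answer is taken "in addition to past follow up reports of quit attempts". Follow-up may be completed by telephone or email, and up to 10 contact attempts are allowed for each assessment.

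**The concern.** The primary analysis in Section VI tests text messaging: TM and TM+NRT against BA and NRT if no interaction is found, or TM against BA otherwise. Only participants in the two TM arms are entered in the messaging platform, so an answer about receiving messages points to exactly the factor under test. Nicotine use, by contrast, hints only at the NRT factor.

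The primary endpoint is an unverified self-report. Exhaled carbon monoxide is sought only from those who report 7-day abstinence, so nothing checks a claimed 24-hour attempt. A telephone interviewer who knows the arm could, without intending it, probe more or try harder to reach one group. The plan already has a blinded second coordinator but does not extend that protection to the primary endpoint, and it places in that person's item list a question that can undo the blinding. Since the Sample size section says the pilot is meant to give preliminary estimates of clinical outcomes, any bias would carry into the planning of later trials.

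**Working it through.** The plan states no figure on this point, so the main check is a comparison of the text, call by call.

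| Call | Blinding stated | Quit-attempt question | Text-message receipt item | Feeds primary outcome |
|---|---|---|---|---|
| Week 1 | Medication use only | Yes | Yes, listed after it | Yes |
| Week 2 | Medication use only | Yes | Yes, listed after it | Yes |
| Week 6 | None | Yes | Yes, listed after it | Yes |
| Week 12 | None | Yes | Not as such; text messaging appears among treatments used, listed after the quit and abstinence items | Yes |

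Reading across:

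1. If the week-1 items are asked as listed, the quit-attempt answer is recorded before any disclosure. That call's answer is not exposed.
2. If the same coordinator calls again, the calls from week 2 onward may be made with knowledge of TM status. The plan fixes neither the caller nor the asking order.
3. For weeks 6 and 12 nothing in the text prevents the unblinded enrolling coordinator from calling.

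**Illustration of size.** The misrecording rates and the true rate are assumptions; the documents give neither.

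- Group size: two arms of 50 with 25% loss (Sample size section), so n = 2 × 50 × 0.75 = 75 per pooled group.
- True quit-attempt rate p in both groups, with no real effect: 30%, 40% or 50%.
- A fraction f of true "no" answers in the TM groups is recorded as "yes", so the observed TM rate is p₂ = p + (1 − p)f, and d = p₂ − p.
- Test: two-sided pooled two-proportion z-test at 5%. With p̄ = (p + p₂)/2, SE₀ = √[2p̄(1 − p̄)/n] and SE₁ = √{[p(1 − p) + p₂(1 − p₂)]/n}, the rejection rate is Φ[(d − 1.96 SE₀)/SE₁] + Φ[(−d − 1.96 SE₀)/SE₁].

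Worked case, p = 0.30 and f = 0.10: p₂ = 0.37, d = 0.07, p̄ = 0.335, SE₀ = 0.0771, SE₁ = 0.0769. The rejection rate is Φ(−1.055) + Φ(−2.876) = 0.146 + 0.002 = 0.148.

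| f | p = 0.30 | p = 0.40 | p = 0.50 |
|---|---|---|---|
| 0.05 | 0.074 | 0.066 | 0.061 |
| 0.10 | 0.148 | 0.115 | 0.094 |

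The result depends on how over-reporting is expressed. If it is set at 5 or 10 percentage points, instead of a fraction of the "no" answers, the same test gives about 9–10% and 23–25%.

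**The case against.** The strongest reply is that the only blinding promised, for medication use at weeks 1 and 2, is largely kept. The medication items come first, so the week-1 answers precede any disclosure. Later exposure needs the same person to call again and to recall the earlier answer. Nor does the text say outright that the blinded coordinator asks every listed item: Section IX.b gives the adverse-event questions at the same contacts to a research coordinator without saying which one. Participants who choose email have no interviewer. The primary item is a closed question, forms carry standard instructions, coordinators are trained, and the contact cap is the same in every arm. The week-12 list already puts quit-attempt and abstinence items ahead of treatment use and satisfaction.

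Most of this stands, and it rules out some stronger readings. A reader might infer that allocation is disclosed before the first quit-attempt answer, or that every later call is necessarily unblinded; the item order, the unnamed callers and the email route do not support that. A reader might also infer that the week-12 endpoint will be collected by the unblinded coordinator; the plan is silent, which permits it but does not say it. Finally, the text-message item is not redundant. Server records (Section IX.a) show messages sent, not received; Section VII.c recognises skipped messages as a fidelity problem; and the platform does not cover the BA and NRT arms.

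What the reply does not answer is the silence on weeks 6 and 12, or the presence of an item that can reveal TM status in calls where a blinded coordinator is specified.

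**Conclusion.** The point holds in limited form and should be fixed. Blinding is stated for one secondary outcome at two time points. The item list for those calls can compromise the blinded coordinator's own later calls, and the week-6 and week-12 calls have no blinding rule although their answers count toward the primary outcome.

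The size cannot be estimated from the documents. The figures of about 6–7% and 9–15% assume misrecording of 5% and 10% of all true "no" answers in the TM groups, a true rate of 30–50%, and 75 per pooled group. They apply the misrecording even to answers given before disclosure or by email, so they should not be read as the trial's actual error rate or as the gain from the fix. Participants know their arm, and their own reporting bias would remain.

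**What to change.** 1. State in Section V.d that the existing second coordinator, blinded to allocation, conducts the telephone outcome assessments at weeks 1, 2, 6 and 12.
2. Take the text-message receipt item off the blinded calls. Either the unblinded coordinator or a separate email/REDCap item collects it, or MobileCommons logs are used for the TM arms. Separate collection is preferable if perceived receipt, or text-message use in the BA and NRT arms, is wanted.
3. State that the listed week-12 order, with quit-attempt and abstinence items before treatment use and satisfaction, is the asking order.

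The cost is a few protocol sentences and a script edit, more calls for the second coordinator (a workload the documents do not size), and a brief extra item or contact for perceived receipt. Relying on logs alone would lose information on receipt and on the two arms without text messaging.

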The PI for this study is on faculty in the MGH Division of General Internal Medicine and is a staff physician at MGH Revere. The proposed trial will be funded by the PI's Career Development (K23) Award from the National Institute on Drug Abuse at the National Institutes of Health, and by a grant to the PI from the MGH Executive Committee on Research Claflin Distinguished Scholars Award.

II. Specific Aim

Research Aim 1: To test, in a 4 arm pilot randomized controlled trial ($N=50/group$), the effect of delivering behavioral smoking cessation content by text message and mailed nicotine replacement therapy on self-reported quit attempts (intentional non-smoking for ≥ 24 hours), pharmacotherapy adherence, and smoking abstinence at the end of treatment.

Hypothesis 1: A 12 week text messaging intervention (up to 30 days pre-quit through 8 weeks post-quit) providing behavioral support will increase the proportion of smokers making a quit attempt compared to smokers receiving no text messaging.

Hypothesis 2: A 12 week text messaging intervention will increase adherence to NRT compared to subjects receiving only 2 weeks of NRT as measured by: (a) duration of NRT use in days and (b) total mg of NRT used.

[figure not shown]
Hypothesis 3: A 12 week text messaging intervention will increase the rate of *biochemically confirmed* past 7-day point prevalent tobacco abstinence at end of treatment compared to subjects receiving no text messaging intervention.

Hypothesis 4: A 12 week text messaging intervention will increase the number of days not smoking compared to subjects receiving no text messaging intervention.

Hypothesis 5: A 12 week text messaging intervention will decrease the number of cigarettes smoked compared to subjects receiving no text messaging intervention

Study Design

Figure. Pilot randomized controlled trial schema

III. SUBJECT SELECTION

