Finally, the text messaging program will be tailored to the individual and MGH. Text messages will include the telephone number for the MGH tobacco cessation counseling services LivingTobacco-Free which accept self-referrals as well as the number for the Massachusetts state quitline.

Smokers receiving the intervention will be sent from 0 and 5 text messages per day. This is the message volume used by most smoking cessation text messaging programs.⁶⁰ Smokers are asked to enter a quit date in the first 30 days after enrollment. Those without a quit date will be sent the practice quit attempt messages. At the end of the practice quit attempt messages subjects will be asked again if they have a quit date in the next 30 days. For those who are ready to quit at time of enrollment, or those who become ready to quit after the practice attempt, up to 5 messages per day are delivered in the 2 weeks leading up to the self-designated quit

date and the 2 weeks after the quit date when they are at greatest risk for relapse.⁶¹ Messages then decrease to 3 messages per week for 8 weeks after the attempt.

b. Drugs used

Subjects randomized to the NRT or TM + NRT arms will be offered nicotine replacement therapy dependent on their smoking patterns and readiness to quit.

Daily smokers planning to quit in the next 30 days will be offered combination nicotine replacement therapy including nicotine patches and nicotine lozenges. Daily smokers will be offered nicotine patches (14 or 21 mg patches) and lozenges (2 or 4 mg lozenges). Smokers who smoke ≥ 10 cigarettes per day will be offered 21 mg patches, those who smoke < 10 cigarettes per day will be offered 14 mg patches. Daily smokers who smoke within 30 minutes of awakening will be also offered the 4 mg lozenges. Daily smokers who smoke > 30 minutes of awakening will be offered 2 mg lozenges. Daily smokers with a prior reaction to adhesives from bandaids or the nicotine patch will be offered lozenges only.

Smokers not planning to quit will be offered one box of lozenges (72 count box of 4 mg or 2 mg lozenges based on time to first cigarette as above per package instructions) to use when they are not smoking during their practice quit attempt⁵³.

The efficacy and safety of mailing nicotine replacement therapy to general population has recently been demonstrated⁵⁵.

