The sample of smokers enrolled in the study will be characterized on baseline measures from the EHR and compared to the population of smokers whom we attempted to contact in order to determine the sample's representativeness to the target population. Variables include demographics, medical history, and practice characteristics. We will also compare baseline characteristics collected from the EHR and from baseline interviews between the 4 randomized groups to determine the success of randomization. The primary outcome analysis will be conducted as intention-to-treat, comparing the primary outcome using chi-square analysis or multiple logistic regression analysis if any baseline factor is significantly imbalanced by group ($p<0.05$) as independent variables. The 4 arm design allows for analysis as a factorial design. We will first test for interaction between the NRT and TM interventions and if no interaction is detected we will test the effect of text messaging using both TM and TM+NRT arms compared to BA and NRT arms. If interaction is present, we will compare the TM arm to BA for our primary analysis. We will secondarily compare the groups in terms of self reported 7 day PPA, biochemically confirmed abstinence, number of days not smoked, use of ≥ 1 evidence based treatments, and cigarettes per day using chi-square or t-tests or logistic or linear regression if groups are imbalanced. We will also compare the TM+NRT group with the NRT group in terms of total days of medication used and total mg of medication used over 2 weeks using linear regression. We will conduct stratified analyses of the primary outcome, 7 day PPA, treatment use and days not smoked by readiness to quit in the next 30 days.

Sample size

Hypothesis 1: A 12 week text messaging intervention (up to 30 days pre-quit through 8 weeks post-quit) providing behavioral support will increase the proportion of smokers making a quit attempt compared to a control group receiving brief advice.

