The sample size for this pilot study is selected to adequately estimate recruitment rates, retention, and to get a preliminary estimate of prevalence of clinical outcomes. We anticipate we can recruit 200 patients by proactive outreach over 12 months. With 50 patients per group and 25% loss to follow-up we will have 81% power to detect a relative risk of self-reported ≥ 24 hour quit attempts of 1.8 for text messaging versus brief advice groups. We base this estimate on meta-analyses of smoking cessation text messaging trials, mostly from community settings or school-based settings, report a relative risk of 1.4 for 7-day point prevalence abstinence and 1.6 for prolonged abstinence measured at six-months.^{8,71}

Hypothesis 2: A 12 week text messaging intervention providing personalized, tailored behavioral support and advice about using nicotine replacement therapy (NRT) plus 2 weeks of NRT mailed to the participant will increase adherence to NRT compared to subjects receiving only 2 weeks of NRT as measured by duration of NRT use in days.

For our secondary outcome of medication adherence, we estimate patients randomized to the NRT will use a mean 9 days of medication based on the offer to mail them 2 weeks of medication for free.⁷² With this sample size, we also have 80% power to detect an increase in days of NRT use from 9 to 12 days in NRT vs. NRT+TM.

Hypothesis 3: A 12 week text messaging intervention will increase the rate of *biochemically confirmed* past 7-day point prevalent tobacco abstinence at end of treatment compared to subjects receiving no text messaging intervention.

We do not expect to have power to detect cessation in this pilot study. With 100 subjects and 25% loss to follow-up we will have 80% power to detect an increase from 6% among the BA & NRT groups to 22% in TM & TM + NRT groups.

Regardless, this pilot study aims to generate an estimate of effect size on cessation at 12 weeks for further studies.

Hypothesis 4: A 12 week text messaging intervention will increase the number of days not smoking compared to subjects receiving no text messaging intervention.

Assuming $\alpha=0.05$ and 25% loss to follow-up, leaving 75 patients, we have 68% power to detect an increase in days not smoked from 0.2 in groups receiving no text messaging (BA & NRT) to 1 in groups receiving text messaging (TM & TM + NRT) assuming a standard deviation of 2.

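### The outcome sentence takes lozenge use from two days per call, in conflict with the survey's 7-day items, and no item counts days on any NRT for patch-plus-lozenge users

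*Combined protocol and SAP*

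**What the plan says.** - **Endpoint.** Hypothesis 2 in section II measures adherence by "a) duration of NRT use in days and (b) total mg of NRT used". Section VI (Data analysis) compares TM+NRT with NRT on "total days of medication used and total mg of medication used over 2 weeks using linear regression".
- **Outcome sentence.** Section V.d (Outcome assessments) sets the week 1 and week 2 medication measure as "number of days patch was used in the last week and number of lozenges used each of the last two days", and adds: "These will be used to calculate total duration of medication". It does not mention mg.
- **Survey items.** The list for the same two calls, immediately below, asks "How many days in the past 7 days did you use a nicotine lozenge" and then "On days when you use lozenge, how many do you use on average". The week 6 list repeats the 7-day lozenge questions. Patch use is asked over 7 days throughout. No listed item asks about the last two days, and none asks about days on either product.
- **Who gets what.** Under section V.b, daily smokers planning to quit are offered patch and lozenge together. "Smokers not planning to quit will be offered one box of lozenges", and daily smokers with a past reaction to adhesives or the patch also get lozenges only.
- **Power.** Section VI (Sample size, Hypothesis 2) claims "80% power to detect an increase in days of NRT use from 9 to 12 days", without a standard deviation.

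**The concern.** The sentence that defines the outcome and the questions that collect it describe different data. Two analysts working from section V.d could build different lozenge totals, and nothing in section VI settles which is right. If the choice is made after the data are seen, it is open to bias.

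Read literally, the outcome sentence leaves most of each week unobserved for lozenges. Patch reports partly cover this for participants using both products. Lozenge-only participants have no patch report. Those not ready to quit are told to use lozenges during practice attempts, which may be short and may fall wholly outside a two-day window.

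The combination-use gap is of another kind. Total days is the quantity on which Hypothesis 2 is powered, yet separate patch-day and lozenge-day counts do not determine it. Analysts cannot repair this later, because the overlap between the two products is never asked.

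**Working it through.** **1. The plan's own figure.** The 80% power cannot be reproduced, because no SD is given for days of NRT use. It can only be solved backwards. With a difference of 12 − 9 = 3 days, 50 × 0.75 = 37.5 per arm and two-sided alpha 0.05 (assumed here; stated only for Hypotheses 4 and 5):

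SD = 3 / [(1.960 + 0.842) × √(2/37.5)] = 4.64 days.

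With 50 per arm the implied SD is 5.35. The rest of this point does not depend on the power figure.

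**2. Coverage under the outcome sentence.** 2 calls × 2 days = 4 days. 4/14 = 28.6%, which leaves 10 days unobserved. A participant with k observed lozenge days (k = 0 to 4) could truly have used lozenges on k to k + 10 days: 0 to 10 if none was seen, 4 to 14 if all four were.

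**3. What extrapolation would cost.** Suppose the count is scaled by 14/4 = 3.5. The estimate can take only the values 0, 3.5, 7, 10.5 or 14. If the four days were a random sample of the 14, and D is the true number of lozenge days, the per-person error is

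SD = 3.5 × √[4 × (D/14) × (1 − D/14) × (10/13)].

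For D = 9 this is about 2.9 days; for D = 12, about 2.1. These values of D are reference points only. The observed days are in fact consecutive, so clustered use would probably make the error larger.

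**4. Coverage under the listed items.** 2 calls × 7 days = 14 of 14 days, if calls fall on schedule. Then:

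- lozenge days = week 1 days + week 2 days;
- lozenge mg = sum over the two weeks of (days × average per use day × 2 or 4 mg);
- patch mg = sum over the two weeks of (patch days × dispensed strength).

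Illustration for one week with invented use: 7 patch days at 21 mg, and 4 lozenge days at 5 per day of 4 mg, give 147 + 80 = 227 mg. Every use input is already asked, and strength is known from dispensing.

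**5. Total days for combination users.** With p patch days and l lozenge days in a week, days on any NRT lie between max(p, l) and min(7, p + l).

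| Patch days | Lozenge days | Days on any NRT |
|---|---|---|
| 3 | 3 | 3 to 6 |
| 4 | 4 | 4 to 7 |
| 5 | 5 | 5 to 7 |
| 7 | 7 | 7 |

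A participant reporting 5 and 5 in both weeks has 10 to 14 days. That 4-day range for one person is wider than the 3-day difference in means the plan is powered for.

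**The case against.** The strongest reply is that the trial already collects what it needs. The 7-day items span the two weeks, give lozenge days directly and, with dispensed strength, give mg. That stands. A reader might infer that the endpoint cannot be obtained at all; the printed survey shows otherwise for lozenge days and for mg. It does not answer the combination-use gap, which exists under either recall window.

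A reader might also infer that lozenge-only durations are capped at 4 days and so cannot reach 9 or 12, or that true values of 9 and 12 would appear as 9 × 4/14 = 2.6 and 12 × 4/14 = 3.4, shrinking the 3-day difference to 0.9. The documents do not support this. It requires reporting the sampled days as the 14-day total, which nothing in the plan says. Scaling by 14/4 under the same even-use assumption returns 9 and 12, leaving noise rather than bias. The calculation method is cited to an outside source not available here. The 9 days is a mean for the NRT group as a whole, and nothing shows that it, or the 12, applies to lozenge-only users.

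Nor is the affected share known. The 32% not ready to quit in the pilot comes from 88 people who opted in after a letter and a single text. This trial recruits mainly by telephone, with advertisement and inpatient referral, and section I puts the national figure at 80%.

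Finally, adherence is a secondary outcome in a pilot, and the primary outcome is untouched. That also stands, and limits the weight of the point.

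**Conclusion.** The point holds as an internal contradiction in section V.d plus one missing item. The outcome sentence observes at most 4 of 14 days for lozenges and would need an unstated extrapolation. The items below it cover all 14, provided calls are made on schedule. The plan does not choose between them and gives no mg formula. The contradiction weighs most on lozenge-only participants, who have no patch data to fall back on.

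Total days on any NRT is not identified for combination users under either version. The uncertainty is up to 2 days a week for someone reporting 5 and 5, and up to 3 for someone reporting 4 and 4.

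No effect on the treatment comparison or on power can be put in numbers from the documents. That would need the SD, the lozenge-only share, the pattern of use and the intended calculation. The change should be made, but the trial does not depend on it.

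**What to change.** 1. In section V.d, name the 7-day items at weeks 1 and 2 as the source for lozenge days. Replace the two-day wording, or keep it only as a supplementary daily count.
2. In section VI, define total mg as patch days × dispensed strength, plus lozenge days × average per use day × dispensed strength, summed over weeks 1 and 2.
3. At each of these calls add one item: on how many of the past 7 days was a patch or a lozenge, or both, used? Define total days as the sum of the two answers.

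The cost is one extra question per call and a few rewritten sentences; no treatment changes. The downside is that recall of lozenge counts over 7 days is less sharp than over two, which is the case for keeping the two-day count as a supplement.

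The fix does not settle when the two weeks begin. Calls are timed from enrollment, while medication is mailed and started only at a quit or practice attempt, so use after week 2 would still be missed. The plan should state that limit.
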